8.2.8. Clinical Safety Laboratory Assessments – Maternal Participants

See [Appendix 2](#) for the list of clinical safety laboratory tests to be performed and the [SoA](#) for the timing and frequency.

The investigator must review the laboratory report, document this review, and record any clinically relevant changes occurring during the study in the AE section of the CRF. Clinically significant abnormal laboratory findings are those which are not associated with the underlying disease, unless judged by the investigator to be more severe than expected for the participant's condition.

All laboratory tests with values considered clinically significantly abnormal during participation in the study should be repeated until the values return to normal or baseline or are no longer considered clinically significant by the investigator or medical monitor.

If such values do not return to normal/baseline within a period of time judged reasonable by the investigator, the etiology should be identified and the sponsor notified.

All protocol-required laboratory assessments, as defined in [Appendix 2](#), must be conducted in accordance with the laboratory manual and the [SoA](#).

If laboratory values from non-protocol-specified laboratory assessments performed at the institution's local laboratory require a change in participant management or are considered clinically significant by the investigator (eg, SAE or AE or dose modification), then the results must be recorded in the CRF.

8.2.9. Biological Samples – All Participants

Serum samples will be used only for scientific research. Each sample will be labeled with a code so that the laboratory personnel testing the samples will not know the maternal or infant participant's identity. Samples that remain after performing assays outlined in the protocol may be stored by Pfizer. Unless a time limitation is required by local regulations or ethical requirements, the samples will be stored for up to 15 years after the end of the study and then destroyed. If allowed by the ICD, stored samples may be used for additional testing to better understand the immune responses to the vaccine(s) under study in this protocol, to inform the development of other products, and/or for vaccine-related assay work supporting vaccine programs. No sequencing of the maternal or infant participant's DNA will be performed.

The maternal participant may request that her (or her infant's) samples, if still identifiable, be destroyed at any time; however, any data already collected from those samples will still be used for this research. The biological samples may be shared with other researchers as long as confidentiality is maintained and no testing of the maternal and infant participant's DNA is performed.

8.2.10. RSV Vaccine Antibody Testing – All Participants

Sera collected will be assayed for RSV A- and RSV B-neutralizing antibody levels, CCI

RSV A- and RSV B-neutralizing antibody levels will be determined and reported as the neutralizing titer. CCI

[REDACTED]

Testing will be performed by a facility designated by Pfizer.

CCI

8.2.13. Blood Volume

8.2.13.1. Maternal Participants: Total Volume of Blood Collected

The total volume of blood collected for antibody assessment over the course of the study will be up to approximately 125 mL depending on when the delivery visit occurs (~25 mL/visit). In addition, sera will be collected at the screening visit for hematology, chemistry, and virology assessments.

8.2.13.2. Infant Participant: Total Volume of Blood Collected

Blood samples will be collected according to the directive 2001/20/EC: Ethical Consideration for Clinical Trials Performed in Children.²⁷

Infant participants will be randomly assigned to 1 of 2 blood sampling schedules.

All infants will have a cord blood sample collected at birth. The cord blood is collected from the umbilical cord vein attached to the placenta after the umbilical cord has been clamped and cut. If cord blood is unavailable, a venous blood sample may be collected from the infant participant up to 24 hours after birth. The infant's weight must be used to determine the volume of blood that can be collected (see [Table 5](#) below). Venous blood samples will also be collected at approximately 1 and 4 months after birth or 2 and 6 months after birth.

The total volume of venous blood collected from each infant participant for antibody assessment will vary depending on the infant's weight at each visit.

The maximum volume of venous blood to be collected will be no more than 15 mL over the course of 12 months.

Table 5. Guideline for Infant Blood Draw

Body Weight (in kg)	Approximate Volume of Blood (in mL) to Be Collected per Blood Draw
<1.3	No blood draw
1.3 to ≤2.4	1.0
>2.4 to ≤3.7	2.0
>3.7 to ≤4.9	3.0
>4.9 to ≤6.2	4.0
>6.2	5.0

8.3. Adverse Events and Serious Adverse Events

The definitions of an AE and an SAE can be found in [Appendix 3](#).

AEs will be reported by the participant (or, when appropriate, by a caregiver, surrogate, or the participant's legally authorized representative).

The investigator and any qualified designees are responsible for detecting, documenting, and recording events that meet the definition of an AE or SAE and remain responsible to pursue and obtain adequate information both to determine the outcome and to assess whether it meets the criteria for classification as an SAE or that caused the participant to discontinue from the study (see [Section 7](#)).

In addition, the investigator may be requested by Pfizer Safety to obtain specific follow-up information in an expedited fashion.

8.3.1. Time Period and Frequency for Collecting AE and SAE Information

The time period for actively eliciting and collecting AEs and SAEs (“active collection period”) for each maternal participant including her fetus begins from the time the maternal participant provides informed consent, which is obtained before participation in the study (ie, before undergoing any study-related procedure and/or receiving investigational product), through and including a minimum of 1 month after the last administration of the investigational product.

In this study, the investigator and site staff will ensure the active elicitation and collection of AEs and SAEs through 1 month after vaccination. From 1 month after vaccination until the maternal participant completes the study, MAEs and SAEs will be collected.

For the infant participant, the time period for actively eliciting and collecting AEs and SAEs (“active collection period”) begins at birth and continues through and including a minimum

of 28 days after birth. From Visit 2 until the last study visit, only AEs of special interest, MAEs, and SAEs, including hospitalizations, will be reported.

CCI

In addition, AEs occurring up to 48 hours after blood draws CCI that are related to study procedures must be reported in the CRF.

For maternal participants who are screen failures, the active collection period ends when screen failure status is determined.

If the participant withdraws from the study and also withdraws consent for the collection of future information, the active collection period ends when consent is withdrawn.

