3. OBJECTIVES, ESTIMANDS, AND ENDPOINTS

3.1. Maternal Participant

Primary Objective Maternal Participant	Estimands	Primary Endpoints Maternal Participant
To describe the safety and tolerability of an RSV vaccine	In maternal participants receiving 1 dose of investigational product: 
 • The percentage of maternal participants reporting local reactions • The percentage of maternal participants reporting systemic events • The percentage of maternal participants reporting AEs • The percentage of maternal participants reporting obstetric complications, medically attended AEs (MAEs), and serious adverse events (SAEs) 	
 • Prespecified local reactions within 7 days after vaccination • Prespecified systemic events within 7 days after vaccination • AEs from the time of vaccination through 1 month after vaccination • Obstetric complications, MAEs, and SAEs throughout the study
Secondary Objective Maternal Participant	Estimands	Secondary Endpoints Maternal Participant
To describe the immune responses elicited by an RSV vaccine	In maternal participants receiving 1 dose of investigational product and in compliance with the key protocol criteria (evaluable participants): 
 • The immune response, estimated by the geometric mean titer (GMT) for RSV A– and RSV B–neutralizing antibody titers. • The immune response, estimated by the geometric mean fold rise (GMFR) from baseline in RSV A– and RSV B–neutralizing antibody titers. • Geometric mean ratio (GMR), estimated by the ratio of the GMT for RSV A– and RSV B–neutralizing antibody titers of the RSV vaccine group and the placebo group. 	
 • RSV A– and RSV B–neutralizing antibody titers measured: 
 • before vaccination • 2 weeks after vaccination • 1 month after vaccination • at delivery

CCI

[figure not shown]

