5.1.1. Inclusion Criteria – Maternal Participants

Age and Sex:

1. Healthy women ≥ 18 and ≤ 49 years of age who are between 24 0/7 and 36 0/7 weeks of gestation on the day of planned vaccination, with an uncomplicated, singleton pregnancy, who are at no known increased risk for complications, and whose fetus has no significant abnormalities observed on ultrasound.

Note: Gestational age must be based upon ultrasound results obtained at ≥ 18 weeks of pregnancy.

Type of Participant and Disease Characteristics:

2. Willing and able to comply with scheduled visits, treatment plan, laboratory tests, and other study procedures.
3. Receiving prenatal standard of care.
4. Had an ultrasound performed at ≥ 18 weeks of pregnancy.

Note: Where an obstetric ultrasound is not performed at ≥ 18 weeks of pregnancy as part of prenatal standard of care, an ultrasound must be performed and reviewed as part of the screening visit.

5. Had a negative urinalysis for protein and glucose at the screening visit (Visit 0). Trace protein in the urine is acceptable if the blood pressure is also normal.
6. Determined by medical history, physical examination, screening laboratory assessment, and clinical judgment to be appropriate for inclusion in the study.

7. Expected to be available for the duration of the study, can be contacted by telephone during study participation, and is willing to give informed consent for her infant to participate in the study.
8. Documented negative human immunodeficiency virus (HIV) antibody, hepatitis B virus (HBV) surface antigen, hepatitis C virus (HCV) antibody, and syphilis tests at the screening visit (Visit 0).

Weight:

9. Body mass index (BMI) of $<40 \text{ kg/m}^2$ at the time of the screening visit.

Informed Consent:

10. Capable of giving signed informed consent as described in [Appendix 1](#), which includes compliance with the requirements and restrictions listed in the informed consent document (ICD) and in this protocol.

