8.10.1.4. Maternal Participants: 1-Month Follow-up Visit (28 to 42 Days After Vaccination)

If delivery occurs before this visit, this visit will not be conducted.

- Ensure that the maternal participant continues to be eligible for the study and meets none of the participant withdrawal criteria as described in [Section 7.2](#).
- Measure vital signs, including oral temperature, seated blood pressure, and heart rate.
- Measure and record weight.
- Perform obstetric examination including but not limited to fundal height, fetal heart tones, and fetal movement.
- Collect a blood sample of approximately 25 mL for serologic assessments.
- Record details of any antenatal steroid treatment, monoclonal antibodies, blood transfusions (eg, whole blood, packed cells), or Rho(D) immune globulin (eg, RhoGam) given since the last visit.
- Record any medication taken to treat an AE since the last visit.
- Record details of any nonstudy vaccinations given since the last visit.
- Complete the maternal participant's source documents.
- Ask the maternal participant to contact the site staff or investigator if a medically attended event (eg, doctor's visit, emergency room visit) or hospitalization occurs.

- Record AEs as described in [Section 8.3](#) and [Section 10.3.3](#).
- The investigator or an authorized designee completes the CRF.

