10.3.1.1. Definition of MAE

An MAE is defined as a nonserious AE that results in an evaluation at a medical facility.

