3.5. Safety Endpoints

3.5.1. Adverse Events

AEs will be captured and reported in accordance with Pfizer reporting standards.

For maternal participants the time period for actively eliciting and collecting AEs and SAEs (“active collection period”) begins from the time the maternal participant provides informed consent, which is obtained before participation in the study (ie, before undergoing any study-related procedure and/or receiving investigational product), through and including a minimum of 1 month (30 days) after the last administration of the investigational product. In this study, the investigator and site staff will ensure the active elicitation and collection of AEs and SAEs through 1 month after vaccination. From 1 month after vaccination until the maternal participant completes the study, MAEs and SAEs will be collected.

For infant participants, the time period for actively eliciting and collecting AEs and SAEs (“active collection period”) begins at birth and continues through and including a minimum

of 28 days after birth. From Visit 2 until the last study visit, only AEs of special interest, MAEs, and SAEs, including hospitalizations, will be reported.

For maternal participants who are screen failures, the active collection period ends when screen failure status is determined. If the participant withdraws from the study and also withdraws consent for the collection of future information, the active collection period ends when consent is withdrawn.

During the active collection period, both nonserious AEs and SAEs are recorded on the case report form (CRF) and will be categorized according to the current version (at the time of reporting) of the Medical Dictionary for Regulatory Activities (MedDRA).

An immediate AE is defined as any AE that occurred within the first 30 minutes after administration of the investigational product for maternal participants.

An MAE is defined as a nonserious AE that results in an evaluation at a medical facility. From Visit 2 (for infant participants) or from 1 month after vaccination (for maternal participants) until the participant completes the study, MAEs and SAEs will be collected.

AEs of special interest for infant participants are major congenital anomalies and developmental delays and are collected from birth through the end of the study (12-month-of-age visit).

CCI

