6.1.1.4. Obstetric Complications, MAEs, and SAEs Throughout the Study

- Analysis set: Safety ([Section 4](#)).
- Analysis methodology: Descriptive summary statistics.
- Intercurrent events and missing data: For participants who discontinue, all collected data will be included; missing AE dates will be imputed as described in Pfizer's Vaccine Statistics Rulebook.
- For each group, number of participants with obstetric complications, MAEs, and SAEs throughout the study (n), %, and 95% CI will be presented for any event, each SOC, and each PT within each SOC, by vaccine group.

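### Obstetric complications are a maternal primary endpoint for the whole study, but the collection rule after 1 month names just MAEs and SAEs, so some nonserious complications need not be recorded as coded events

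*Protocol*

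**What the plan says.** **Endpoint.** Protocol 3.1 lists as a maternal primary endpoint "Obstetric complications, MAEs, and SAEs throughout the study". SAP 3.1.1 repeats it, and SAP 6.1.1.4 plans the table: "number of participants with obstetric complications, MAEs, and SAEs throughout the study (n), %, and 95% CI will be presented", by system organ class and preferred term within vaccine group.

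**Collection.** All AEs are elicited from consent for a "minimum of 1 month (30 days) after the last administration of the investigational product" (SAP 3.5.1). After that, Protocol 8.3.1 says: "From 1 month after vaccination until the maternal participant completes the study, MAEs and SAEs will be collected". SoA footnote i and SAP 3.5.1 carry the same sentence. The delivery and postdelivery visits (Protocol 8.10.1.5 to 8.10.1.8) give no AE rule of their own; they refer back to Sections 8.3 and 10.3.3.

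**Definitions.** "An MAE is defined as a nonserious AE that results in an evaluation at a medical facility" (Protocol 10.3.1.1). Under Protocol 10.3.2, a complication during a hospital stay is an AE, and it is serious if it prolongs the stay or meets another seriousness criterion. Neither document defines obstetric complication. Protocol 9.4.2.1 leaves definition and identification to the sponsor's study clinician before unblinding.

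**Other obstetric data.** The pregnancy is followed to its end (Protocol 8.3.1.2). Scheduled obstetric examinations stop at the 1-month visit, but pregnancy outcome data include mode of delivery, cesarean type, outcome, and a yes/no item on delivery complications (SAP 3.5.6). They are summarized under SAP 6.6.5.

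**The concern.** The endpoint treats obstetric complications as a category in its own right, but the rule that tells sites what to record after 1 month does not mention it. For infants the corresponding rule does carry the special category forward: AEs of special interest are named beside MAEs and SAEs after Visit 2.

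Two things are at stake. First, late pregnancy, labor and delivery mostly fall after the all-AE period, so the reported percentage of women with an obstetric complication may be too low. In a descriptive study the percentages and their intervals are themselves the result. Second, completeness would depend on when a woman was vaccinated, because that decides whether her delivery falls inside the all-AE period.

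**Working it through.** **1. Which events fall through.** Take a complication that starts more than 1 month after vaccination and follow the definitions.

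- It prolongs the stay or meets another serious criterion: it is an SAE and is collected.
- It is nonserious and sends the woman to a medical facility: it is an MAE and is collected.
- It is nonserious and arises while she is already admitted for delivery, or is noted at a prenatal visit that was due anyway: it is an AE, but the evaluation did not plainly result from it. The post-1-month rule does not require it, although a site could reasonably read the MAE definition either way.

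The third group is the gap. Later identification by the sponsor's clinician cannot recover an event that the site was not asked to record. A yes to delivery complications shows that something happened but has no preferred term, while the SAP 6.1.1.4 table needs one. Neither document says that a yes must be given a coded term, or that it is left out of that table.

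**2. How many women deliver after the cut-off.** The documents state no such share and no expected gestational age (GA) at delivery, so there is no plan figure to reproduce.

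Inputs from the documents:
- vaccination "between 24 0/7 and 36 0/7 weeks of gestation on the day of planned vaccination" (Protocol 5.1.1);
- all-AE period of at least 30 days (SAP 3.5.1);
- 1-month visit "28 to 42 Days After Vaccination", so day 42 is the late alternative cut-off.

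Assumptions: vaccination GA uniform over 24-36 weeks (the protocol monitors the spread but sets no quotas); delivery GA normal with mean μ = 38.5-40 weeks and SD σ = 1.5-2 weeks.

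Formula for cut-off day d, with S the standard normal upper tail and g the vaccination GA:

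share = average over g from 24 to 36 of S((g + d/7 − μ)/σ) / S((g − μ)/σ).

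Hand check with no spread in delivery GA, where share = (μ − d/7 − 24)/12, at μ = 39:
- d = 30: (39 − 4.286 − 24)/12 = 10.714/12 = 0.893
- d = 42: (39 − 6 − 24)/12 = 9/12 = 0.750

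Results with spread (σ = 1.5 / σ = 2):

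| Mean delivery GA, weeks | After day 30 | After day 42 |
|---|---|---|
| 38.5 | 0.845 / 0.837 | 0.708 / 0.707 |
| 39 | 0.880 / 0.869 | 0.749 / 0.746 |
| 39.5 | 0.911 / 0.897 | 0.789 / 0.784 |
| 40 | 0.937 / 0.922 | 0.828 / 0.820 |

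The ranges are therefore 84-94% after day 30 and 71-83% after day 42.

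**3. Sensitivity to the enrollment pattern** (σ = 1.5, μ = 38.5-40). Enrollment weighted linearly toward early GA gives 95-99% after day 30. Weighted toward late GA it gives 74-89% after day 30 and 53-71% after day 42.

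**4. Dependence on GA at vaccination** (σ = 1.5, μ = 39-40):

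| Vaccination GA | Deliver after day 30 | Deliver after day 42 |
|---|---|---|
| 24 to <33 weeks | about 99% or more | 93-98% |
| 33 to 36 weeks | 55-76% | 20-39% |

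For example, a woman vaccinated at 36 weeks who delivers at 39 weeks does so on day 21 (3 × 7), inside the all-AE period. One vaccinated at 26 weeks who delivers at 39 weeks does so on day 91 (13 × 7). The same nonserious delivery complication must be recorded for the first and need not be for the second.

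**The case against.** The strongest reply is that capture after 1 month is broad.

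- Serious and medically attended events are collected to the end of the study, and the protocol tells sites to treat doubtful hospitalizations as serious.
- Women must be receiving prenatal care and are asked at most visits to report medically attended events. A site that reads the MAE definition generously would record most complications.
- The maternal sentence does not contain the word only (the infant sentence does), and the active period is a minimum.
- The CRF table in Protocol 10.3.3 asks for all nonserious AEs without a time limit.
- The study reference manual and CRF, which are not among the documents, may settle the matter.

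Much of this stands. It limits the gap to nonserious complications not counted as MAEs, and it rules out saying that obstetric data stop at 1 month. It does not close the gap. Protocol 8.3.1.2 ties CRF recording of AEs to the active collection period, and no passage requires an obstetric complication to be collected as such afterwards. Where the text permits two readings, capture can differ between sites.

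A reader might also infer that the delivery-complications item is excluded from SAP 6.1.1.4. The documents do not say so; that section names no source at all.

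Finally, assignment is randomized and the study is observer-blinded, so incomplete capture should be similar across arms. That also stands. The effect is on the absolute percentages.

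**Conclusion.** The endpoint and the collection rule do not match, and the mismatch concerns one component of a primary safety endpoint. Followed as written, the plan need not record as coded events those nonserious complications that arise after 1 month and do not clearly result in a facility evaluation. The reported percentages may be an undercount, with completeness that varies with GA at vaccination.

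Most women would deliver after the all-AE period: 84-94% after day 30 and 71-83% after day 42, with uniform vaccination GA, mean delivery at 38.5-40 weeks and SD 1.5-2. Delivery GA and enrollment spread are assumptions, not figures from the plan. The conclusion that it is most women survives the skewed enrollment patterns tried.

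Two stronger readings are not supported. One is that a similar share of complications would be missed: the figures count women delivering late, serious and medically attended events are still collected, and the documents give no rate for the remainder. The other is that the maternal primary safety objective goes unmeasured or that the vaccine-placebo comparison is biased. Local reactions, systemic events, 1-month AEs, MAEs and SAEs are unaffected, and randomization should balance the gap across arms.

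**What to change.** - In Protocol 8.3.1, SoA footnote i and SAP 3.5.1, state that from 1 month after vaccination to the final visit the events collected are *obstetric complications (regardless of seriousness or medical attendance), MAEs, and SAEs*.
- In SAP 6.1.1.4, name the CRF source of the obstetric-complication counts, and have a coded term recorded for each yes to delivery complications. If full capture was always intended, this puts it in the text.

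The cost is document wording and CRF completion guidance. Sites would record a few more nonserious events at visits already held, and the reported percentage would be somewhat higher.
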